Appendix: definitions

Clinical outcome measures

Primary outcome measure

Composite of pneumonia, re-intubation, or death within 30 days of randomisation.

Pneumonia

Care will be taken to distinguish between tracheal colonisation, upper respiratory tract infections and early onset pneumonia. Pneumonia must meet the following criteria:

Two or more serial chest radiographs with at least one of the following features (one radiograph is sufficient for patients with no underlying pulmonary or cardiac disease):

- a) new or progressive and persistent infiltrate
- b) consolidation
- c) cavitation

AND at least one of the following:

- a) fever ($>38^{\circ}\text{C}$) with no other recognised cause
- b) leucopaenia ($< 4 \times 10^9/\text{L}$) or leucocytosis ($>12 \times 10^9/\text{L}$)
- c) for adults >70 years old altered mental status with no other cause

AND at least two of the following:

- a) new onset of purulent sputum or change in character of sputum or increased respiratory secretions or increased suctioning requirements
- b) new onset or worsening cough or dyspnoea, or tachypnoea
- c) rales or bronchial breath sounds
- d) worsening gas exchange (hypoxia, increased oxygen requirement, increased ventilator demand)

Endotracheal re-intubation

Re-insertion of an endotracheal tube after the patient has been extubated following the completion of the index surgical procedure. Endotracheal extubation is defined as an intentional clinical decision to remove an endotracheal tube. Extubation does not include accidental or inadvertent removal of an endotracheal tube. Re-intubation does not include intubation and anaesthesia for subsequent surgical procedures within the follow-up period, unless the patient is not extubated at the end of the later surgical procedure.

Secondary outcome measures (listed alphabetically)

Acute Kidney Injury

According to the KIDGO consensus definition of moderate or severe acute kidney injury (2012):

- a) a two-fold increase in serum creatinine compared the preoperative baseline measurement
- b) or an increase in serum creatinine $\geq 354 \mu\text{mol/L}$ ($\geq 4.0 \text{ mg/dL}$) with an acute rise of $> 44 \mu\text{mol/L}$ (0.5 mg/dL)
- c) or oliguria of $< 0.5 \text{ ml/kg/hour}$ for twelve consecutive hours
- d) or the initiation of new renal replacement therapy

Note: Cannot be diagnosed in patients with existing end stage renal failure.

Acute psychosis or delirium

An acute episode of severe confusion or personality change, which may result in hallucinations or delusional beliefs in the absence of a pre-existing diagnosis, which may account for the clinical symptoms and signs.

Acute respiratory distress syndrome

According to the Berlin consensus criteria (2012):

- a) Within one week of a known clinical insult or new worsening respiratory symptoms
- b) AND bilateral opacities on chest imaging, not fully explained by effusions, lobar/lung collapse, or nodules
- c) AND respiratory failure not explained by cardiac failure or fluid overload (requires objective assessment e.g. echocardiogram to exclude hydrostatic oedema if no risk factors are present)
- d) AND supplemental oxygenation (requires correcting if altitude >1000m):
 - Mild: $\text{PaO}_2:\text{FiO}_2$ 26.7-40.0 kPa with PEEP or CPAP $\geq 5\text{cmH}_2\text{O}$
 - Moderate: $\text{PaO}_2:\text{FiO}_2$ 13.3-26.6 kPa with PEEP $\geq 5\text{cmH}_2\text{O}$
 - Severe: $\text{PaO}_2:\text{FiO}_2 \leq 13.3$ kPa with PEEP $\geq 5\text{cmH}_2\text{O}$

Anastamotic leak

Demonstrated at laparotomy or by contrast enhanced radiograph or CT scan.

Aspiration pneumonitis

Acute lung injury after the inhalation of gastric contents.

Bowel infarction

Demonstrated at laparotomy.

Bronchospasm

Newly detected expiratory wheeze treated with bronchodilators.

Cardiac events

Myocardial infarction

Increase in serum cardiac biomarker values (preferably cardiac troponin) with at least one value above the 99th percentile upper reference limit and at least one of the following criteria:

- a) symptoms of new ischaemia
- b) new or presumed new significant ST segment or T wave ECG changes or new left bundle branch block
- c) development of pathological Q waves on ECG
- d) radiological or echocardiographic evidence of new loss of viable myocardium or new regional wall motion abnormality
- e) identification of intracoronary thrombus at angiography or autopsy

Arrhythmia

ECG evidence of cardiac rhythm disturbance.

Cardiac arrest with successful resuscitation

Cardiac arrest according to UK Resuscitation Council definition. Successful resuscitation is defined as return of spontaneous circulation for at least one hour.

Cardiogenic pulmonary oedema

Appropriate clinical history and examination with consistent chest radiograph.

Infective complications

Infection, source uncertain

Strong clinical suspicion of infection but the course has not been confirmed. Requires two or more of the following criteria:

- a) core temperature $<36^{\circ}\text{C}$ or $>38^{\circ}\text{C}$
- b) white cell count $>12 \times 10^9/\text{L}$ or $<4 \times 10^9/\text{L}$
- c) respiratory rate >20 breaths per minute or $\text{PaCO}_2 < 4.5 \text{ kPa}$
- d) pulse rate >90 beats per minute

Urinary tract infection

This is a simplified version of the CDC criteria taken from the ESA-ESICM consensus on perioperative outcome measures (Jammer et al. 2014).

Urinary tract infection is defined as a positive urine culture of $\geq 10^5$ colony forming units per ml with no more than two species of micro-organisms AND with at least one of the following signs or symptoms:

- a) fever ($>38^{\circ}\text{C}$)
- b) urgency
- c) frequency
- d) dysuria
- e) suprapubic tenderness
- f) costo-vertebral angle pain or tenderness with no other recognised cause

Surgical site infection (superficial)

A superficial surgical site infection must meet the following criteria:

Infection occurs within 30 days after the operative procedure AND involves only skin and subcutaneous tissue of the incision AND patient has at least one of the following:

- a) purulent drainage from the superficial incision;
- b) organisms isolated from an aseptically obtained culture of fluid or tissue from the superficial incision;
- c) at least one of the following signs or symptoms of infection: pain or tenderness, localised swelling, redness, or heat, and superficial incision is deliberately opened by surgeon, unless incision is culture-negative;
- d) diagnosis of superficial incisional surgical site infection by the surgeon or attending physician.

Surgical site infection (deep)

A deep incisional surgical site infection must meet the following criteria:

Infection occurs within 30 days after the operative procedure AND involves deep soft tissues (e.g., fascial and muscle layers) of the incision AND patient has at least one of the following:

- a) purulent drainage from the deep incision but not from the organ/space component of the surgical site
- b) a deep incision spontaneously dehisces or is deliberately opened by a surgeon when the patient has at least one of the following signs or symptoms: fever ($>38^{\circ}\text{C}$) or localised pain or tenderness, unless incision is culture-negative
- c) an abscess or other evidence of infection involving the deep incision is found on direct examination, during reoperation, or by histopathological or radiologic examination

- d) diagnosis of a deep incisional surgical site infection by a surgeon or attending physician

An infection that involves both superficial and deep incision sites should be classified as a deep incisional surgical site infection.

Surgical site infection (organ/space)

An organ/space surgical site infection involves any part of the body, excluding the skin incision, fascia, or muscle layers that is opened or manipulated during the operative procedure. An organ/space surgical site infection must meet the following criteria:

Infection occurs within 30 days after the operative procedure AND appears related to the previous surgery AND the infection involves any part of the body, excluding the skin incision, fascia, or muscle layers opened or manipulated during the operative procedure AND patient has at least one of the following:

- a) purulent drainage from a drain that is placed through a stab wound into the organ/space;
- b) organisms isolated from an aseptically obtained culture of fluid or tissue in the organ/ space;
- c) an abscess or other evidence of infection involving the organ/space that is found on direct examination, during reoperation, or by histopathologic or radiologic examination;
- d) diagnosis of an organ/space surgical site infection by a surgeon or attending physician.

Laboratory-confirmed bloodstream infection

Requires at least one of the following criteria:

- a) Patient has a recognised pathogen cultured from one or more blood cultures and the organism cultured from blood is not related to an infection at another site.
- b) Patient has a fever ($>38^{\circ}\text{C}$), chills, or hypotension and at least one of the following:
 - a. Common skin contaminant is cultured from two or more blood cultures drawn on separate occasions;
 - b. Common skin contaminant is cultured from at least one blood culture from a patient with an intravascular line, and the physician institutes appropriate antimicrobial therapy;
 - c. Positive antigen blood test.

Perforated viscus

Demonstrated at laparotomy or by contrast enhanced radiograph or CT scan. For example perforated bowel, gall bladder etc.

Pleural effusion

Radiological evidence of significant fluid accumulation in the pleural cavity. Most commonly this will be detected using a chest radiograph or an ultrasound scan.

Pneumothorax

Air in the pleural cavity with no visceral bed surrounding the visceral pleura. Usually results from damage to the pleural membranes or lung tissue.

Postoperative haemorrhage*Gastro-intestinal bleed*

Unambiguous clinical evidence or endoscopy showing blood in gastro-intestinal tract.

Other postoperative haemorrhage

Overt blood loss, not from the gastro-intestinal tract, requiring transfusion of two or more units of blood in two hours.

Pulmonary embolism

A new blood clot or thrombus within the pulmonary arterial system identified by computed tomography pulmonary angiogram (CTPA) with an appropriate clinical history.

Stroke

Clinical diagnosis with confirmation by computed tomography (CT) scan.

Definitions of pre-defined adverse events related to CPAP

Interface intolerance due to excessive air leak

Air leaks associated with delivery device sufficient to prevent effective CPAP. Subjective assessment by clinician.

Pain

Pain associated with contact of delivery device against the skin, sufficient to prevent effective CPAP. Subjective assessment of severity by the investigator.

Cutaneous pressure sore or pressure area

Pressure sore or pressure area associated with contact of the delivery device against the skin. Assessment of severity to be completed by investigator and reported on page two of the supplementary adverse event form according to Waterlow grading¹⁶:

- a) Grade 1: discolouration of intact skin, not affected by light pressure
- b) Grade 2: partial thickness skin loss/damage involving the dermis or epidermis
- c) Grade 3: Full thickness skin loss/damage involving the subcutaneous tissue but not the underlying fascia.
- d) Grade 4: Full thickness skin loss/damage with extensive destruction and necrosis of the underlying tissue.

Claustrophobia

Claustrophobia associated with the delivery device sufficient to prevent effective CPAP. Subjective assessment of severity by investigator.

Oronasal dryness

Oronasal dryness associated with delivery device sufficient to prevent effective CPAP. Subjective assessment of severity by the investigator.

Hypercapnia

Hypercapnia *directly resulting* from CPAP and sufficient to prevent effective CPAP. This should not include hypercapnia not directly caused by CPAP. Subjective assessment by investigator and to record peak PaCO₂ on page two of the supplementary adverse event form.

Haemodynamic instability

Systolic blood pressure of less than 70 mmHg *or* need for inotropic drugs to maintain systolic blood pressure higher than 85 mmHg for two hours or more, *or* electrocardiogram evidence of ischemia or significant ventricular arrhythmias.

Vomiting

Vomiting, which is sufficient to prevent effective CPAP. Subjective assessment of severity by investigator.

Aspiration of gastric contents

Inhalation of regurgitated gastric contents directly related to CPAP.

Other definitions

Active cancer

A current diagnosis of cancer excluding non-melanoma skin cancers. A previous diagnosis of cancer where the patient underwent curative treatment with remission is not considered active cancer. A surgical procedure where the indication is a presumed diagnosis of cancer, but which has not yet been confirmed with histology, should be considered active cancer.

Cancer surgery

Intended to be a curative treatment

The surgical procedure is intended to cure the cancer.

Intended to be palliative treatment

The surgical procedure is not intended to cure the cancer. For example surgical debulking in metastatic disease, partial removal of a tumour or for the purpose of pain or other symptom control.

End of surgery

Completion of surgery. Usually marked by suturing of the wound and application of dressing(s).

Intraoperative recruitment manoeuvre

A technique used by the anaesthetist to transiently increase the transpulmonary pressure. This is usually by increasing tidal volume or inspiratory pressure for at least one breath.

Levels of care after surgery

Level 3 care: Critical care unit

A clinical area capable of providing invasive mechanical ventilation or support to at least two organ systems.

Level 2 care: Critical care unit or step-down unit

A clinical area capable of providing support to a single organ system, but not including invasive mechanical ventilation, which is considered level 3 care.

Post-anaesthesia care unit (PACU)

Short-stay clinical area dedicated to caring for patients that are recovering from anaesthesia. If the PACU is providing level 2 care then level 2 care should be recorded on the CRF.

Surgical ward

Hospital ward environment not offering single-organ support or dedicated to patients recovering from anaesthesia.

Critical care unit admission

Either level two or level three care, as defined above.

Open surgical technique

Open abdominal surgery is usually distinguished from laparoscopic by the fact that for laparoscopic surgery the incision is only large enough to remove the resected specimen. Some procedures may involve the use of a laparoscope as well as an open incision, where the incision is larger than required to remove the specimen – this is considered open surgery.

Preoperative oxygen saturation (SpO₂)

Pulse-oximetry on room air before surgery.

Primary hospital admission

The hospital admission for elective surgery during which the participant was randomised as part of the PRISM trial. The duration of the primary hospital stay

should be calculated from the date of randomisation.

Respiratory support

Invasive mechanical ventilation

Positive pressure ventilation via an endotracheal tube or supraglottic airway device.

Non-invasive mechanical ventilation

Positive pressure mechanical ventilation via a face-mask, hood or helmet, or nasal device. However, Continuous Positive Airway Pressure (CPAP) is not considered non-invasive mechanical ventilation.

High flow nasal oxygen

Humidified oxygen therapy delivered via large-bore nasal prongs at flow rates greater than 50 litres per minute.

Maximum positive end expiratory pressure (PEEP) during surgery

The maximum pressure, above atmospheric pressure, that exists at the end of expiration and provided by mechanical ventilation.

Maximum set tidal volume (V_t) during surgery

The maximum volume of air displaced between inspiration and expiration during mechanical ventilation as set on the ventilator.

Start of surgery

Time of the induction of anaesthesia before the surgical procedure.

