5.5 Safety objectives

To determine the safety and tolerability of routine postoperative CPAP.

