5.6 Safety outcome measures

Safety outcomes will quantify harm associated with CPAP (appendix). The following pre-defined adverse events will be measured within 24 hours of the end of surgery in patients in the intervention group only:

- Interface intolerance due to excessive air leaks
- Pain
- Cutaneous pressure sore or pressure area
- Claustrophobia
- Oro-nasal dryness
- Hypercapnia
- Haemodynamic instability
- Vomiting
- Aspiration of gastric contents
- Other harm assessed as probably or definitely related to CPAP

A full list of definitions is available in the appendix.

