12. SAFETY REPORTING

12.1 Adverse Events (AE)

An AE is an untoward medical occurrence in a PRISM trial participant. This may be any unfavourable and unintended sign, symptom or disease. It is expected that patients undergoing major abdominal surgery may often suffer medical complications, up to and including death. It follows that a large number of PRISM trial participants will experience complications of surgery, which are completely unrelated to the trial intervention. In the PRISM trial, only AEs clearly related to the use of CPAP will be reported. It is anticipated that almost all of these will fall under one of the following predefined categories:

- Interface intolerance due to excessive air leaks
- Pain
- Cutaneous pressure sore or pressure area
- Claustrophobia
- Oro-nasal dryness
- Hypercapnia
- Haemodynamic instability
- Vomiting
- Aspiration of gastric contents

The Principal Investigator (or suitably qualified nominee) is responsible for confirming the relatedness of any AE to the trial intervention. If an AE occurs the clinician responsible for the patient should decide whether it is safe to continue CPAP, with or without modification, or whether CPAP should be discontinued.

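### Hypercapnia and vomiting enter their named safety counts only if they prevent effective CPAP, so those two counts understate CPAP-related harm

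*Protocol*

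**What the plan says.** The safety objective in section 5.5 is "To determine the safety and tolerability of routine postoperative CPAP". Section 5.6 turns this into outcomes: "Safety outcomes will quantify harm associated with CPAP", measured "within 24 hours of the end of surgery in patients in the intervention group only". It lists nine named events and a tenth item for other harm judged probably or definitely CPAP-related, and refers to the appendix for definitions.

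In the appendix, hypercapnia must result "from CPAP and sufficient to prevent effective CPAP. This should not include hypercapnia not directly caused by CPAP". The vomiting entry is "Vomiting, which is sufficient to prevent effective CPAP", followed only by a note that severity is the investigator's subjective assessment. Air leak has the same condition ("Air leaks associated with delivery device sufficient to prevent effective CPAP"), as do pain, claustrophobia and oronasal dryness. Pressure sore, haemodynamic instability and aspiration do not.

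Section 12.1 limits reporting to adverse events clearly linked to CPAP. It then says that, when one occurs, the responsible clinician "should decide whether it is safe to continue CPAP, with or without modification, or whether CPAP should be discontinued". Section 12.2 asks sites to record all adverse events on the supplementary form. Section 12.3 defines serious events by relatedness and seriousness alone.

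**The concern.** Whether an event harmed the patient and whether it defeated delivery of the treatment are separate questions. For an air leak they nearly coincide, because a leak matters mainly through lost delivery. For hypercapnia and vomiting they do not: carbon dioxide retention caused by CPAP, or vomiting related to it, is a harm whether or not effective CPAP goes on. With prevention of effective CPAP built into the case definition, the category leaves out patients who had the harm and stayed effectively exposed.

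The safety objective has no other dedicated measure of these two harms, and they are collected in one arm only, so the category counts will be read as the rates at which CPAP causes them. Section 14.3 gives the DMEC a mainly safety role based on adverse event review. The protocol does not define effective CPAP, the assessment is stated to be subjective, and section 7.4 leaves delivery and monitoring to local policy. Sites could therefore draw the line in different places.

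**Working it through.** No design figure is affected, so the check is a comparison of definitions.

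**Step 1. Which of the ten items in section 5.6 require that effective CPAP was prevented?**

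| Item | Condition in appendix? |
|---|---|
| Air leak | Yes |
| Pain | Yes |
| Pressure sore or area | No (graded 1 to 4) |
| Claustrophobia | Yes |
| Oronasal dryness | Yes |
| Hypercapnia | Yes, plus direct causation by CPAP |
| Haemodynamic instability | No (blood pressure, inotropes or ECG) |
| Vomiting | Yes, with no relatedness wording |
| Aspiration | No (direct relation to CPAP suffices) |
| Other related harm | No |

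Six of the nine named events carry the condition (9 − 3 = 6), and four of the ten items do not (10 − 6 = 4).

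**Step 2. For which of the six is the condition out of place?** Section 5.5 covers tolerability as well as safety. For air leak, pain from the device, claustrophobia and dryness, preventing effective CPAP is a reasonable tolerability threshold. That leaves two, hypercapnia and vomiting (6 − 4 = 2).

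**Step 3. Follow one patient through the text.** CPAP directly causes a rise in PaCO2, and CPAP remains effective to the end of the course.

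- Section 12.1: clearly related to CPAP, so reportable, and CPAP may continue.
- Appendix, hypercapnia: causation met, prevention of effective CPAP not met, so not a hypercapnia event.
- Section 5.6, other harm: possibly, if a milder form of a named event counts as other.
- Section 7.7, 24-hour data: the answer to the hypercapnia Y/N item is No if the appendix definition is applied, and there is no other-harm item in that list.
- Section 12.2: to be recorded if it is an adverse event, but the section does not say whether section 12.1 or the appendix decides that.
- Section 12.3: reportable only if it also meets a seriousness criterion.

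A patient with CPAP-related vomiting follows the same path. The named category excludes the event, and no text clearly says where it goes instead.

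**Step 4. Is delivery failure captured elsewhere?** Largely. Section 7.8 lists CPAP for under four hours and significant interruption as protocol deviations. Keeping the delivery condition inside the harm definition is therefore not needed to detect shortened or interrupted treatment.

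**The case against.** The strongest reply is that these events are not lost. Section 5.6 has a catch-all without the condition, section 12.1 makes relatedness the reporting test and says only that nearly all events will fit the named categories, section 12.2 asks for all adverse events, and serious related harm is reportable whatever happened to CPAP. This largely stands. A reader might infer that harm in a patient whose CPAP continued goes unrecorded; the documents do not support that. They support exclusion from the named category and uncertainty about where the event is placed. The catch-all is a weak safeguard, because it covers other harm and is absent from the lists in sections 7.7 and 12.1.

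A reader might also infer that the safety outcome as a whole measures treatment failure and not harm. It does not: four of the ten items are free of the condition, including aspiration, a possible serious consequence of vomiting. For four of the other six, the condition fits the tolerability half of the objective.

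Third, preventing effective CPAP is not the same as stopping it. An event may make CPAP ineffective and the clinician may still continue or modify it. So the definition does not make the count depend on a decision to stop, and the appendix and section 12.1 can operate together for events that meet the threshold. The mismatch is confined to related events that fall below it.

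Fourth, section 7.7 lists peak PaCO2 beside the hypercapnia Y/N item as well as on the adverse event form. It does not say whether the value is entered only after a Yes, so its loss is likely but not established.

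Finally, the DMEC also reviews other safety data, and death, pneumonia, re-intubation and mechanical ventilation are compared between arms. Serious consequences would remain visible.

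**Conclusion.** The point holds for hypercapnia and vomiting. As defined, their category counts omit CPAP-related events in patients whose CPAP stayed effective. This understates harm and does not fit the purpose stated in section 5.6 or the relatedness rule in section 12.1. It affects two of ten safety items and leaves the primary outcome, sample size and error rates untouched.

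The undercount cannot be quantified. The protocol gives neither the frequency of these events nor the share in which CPAP stayed effective, and any figure would rest on invented rates. The direction is clear provided that sites apply the appendix definitions as written and that at least some related events leave CPAP effective. If every such event were entered under other harm, the total would be right but the two category rates would still be too low.

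**What to change.** For hypercapnia and vomiting only:

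- Define the event by its relation to CPAP. Hypercapnia keeps its existing direct-causation wording. Vomiting must gain explicit wording that it is clearly related to CPAP, the test already set in section 12.1. Without that, removing the condition would leave the bare word, and any vomiting in the 24 hours after laparotomy could be counted, in the intervention arm alone and with no comparator.
- Move the condition to a separate Y/N field recording whether the event prevented effective CPAP. Harm and tolerability are then both reported. Events marked Yes still give the count under the present condition, with vomiting limited to events related to CPAP.
- Record peak PaCO2 for every CPAP-related hypercapnia event. The definition would otherwise carry no indication of severity.

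Leave air leak, pain, claustrophobia and oronasal dryness as they are. Reconcile section 5.6, section 12.1 and the appendix so that a site can tell where each related event is entered.

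The cost is a change to two appendix definitions, one extra form field and somewhat higher reported adverse event rates. No rule on continuing, modifying or stopping CPAP changes.
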